4.1.7 Storage conditions

BI 836880 vials and Diluent vials, which will be provided by the sponsor and/or a CRO appointed by the sponsor must be kept in their original packaging and in secure limited access storage area according to the recommended storage conditions on the medication label. The Investigator, the Pharmacist, or other personnel allowed to store and dispense.

The Investigator or pharmacist or investigational drug storage manager will be responsible for ensuring that the investigational product used in the study is securely maintained as specified by the sponsor and in accordance with the applicable regulatory requirements.

A temperature log must be maintained for documentation.

For details concerning the preparation of the infusion solution of BI 836880, please refer to the 'instructions for pharmacists' filed in the ISF.

4.1.8 Drug accountability

The Investigator or pharmacist or investigational drug storage manager will receive the investigational drugs delivered by the Sponsor when the following requirements are fulfilled:

- Approval of the trial protocol by the IRB / ethics committee,
- Availability of a signed and dated clinical trial contract between the Sponsor and the head of the investigational site,
- Approval/notification of the regulatory authority, e.g. competent authority,
- Availability of the curriculum vitae of the principal Investigator,
- Availability of a signed and dated clinical trial protocol,
- Availability of the proof of a medical license for the principal Investigator.

Page 35 of 99

Proprietary confidential information © 2019 Boehringer Ingelheim International GmbH or one or more of its affiliated companies

The Investigator or pharmacist or investigational drug storage manager will receive the investigational drugs delivered by the Sponsor after IRB / ethics committee approval of the trial and completion of a clinical trial contract between the Sponsor and the Head of Trial Center.

The Investigator or pharmacist or investigational drug storage manager must maintain records of the product's delivery to the trial site, the inventory at the site, the use by each patient, and the return to the Sponsor or alternative disposal of unused products.

These records will include dates, quantities, batch / serial numbers, expiry ('use- by') dates, and the unique code numbers assigned to the investigational product and trial patients. The Investigator / pharmacist / investigational drug storage manager will maintain records that document adequately that the patients were provided the doses specified by the CTP and reconcile all investigational products received from the Sponsor. All remaining drug supplies received at a respective study site will be destroyed at site. Partially used vials will be destroyed after preparation infusion; unused medication and Diluent will be destroyed after expiry or at the end of study before closing the site.

4.2 CONCOMITANT THERAPY, RESTRICTIONS, AND RESCUE TREATMENT

Concomitant (non-oncological) therapies starting or changing during the course of the trial should be recorded in the electronic Case report Form (eCRF).

4.2.1 Rescue medication, emergency procedures, and additional treatment(s)

Rescue medication to reverse the action of BI 836880 is not available. Potential side effects of BI 836880 have to be treated symptomatically. Symptomatic treatments of side effects or tumor-associated symptoms are allowed. Concomitant medications, or therapy to provide adequate care, may be given as clinically necessary. There are no special emergency procedures to be followed.

4.2.2 Restrictions

4.2.2.1 Restrictions regarding concomitant treatment

Previous anti-cancer therapy must have been discontinued before first administration of BI 836880 and the patient must have recovered from all clinical relevant reversible toxicities (see exclusion criteria in Section 3.3.3).

Concomitant anti-cancer therapy is not allowed.

Radiotherapy for local symptom control of non-target lesions can be allowed after discussion between the investigator and the sponsor. The irradiated area cannot be used for response assessment.

13 Mar 2019

Trial Protocol

Page 36 of 99

Proprietary confidential information © 2019 Boehringer Ingelheim International GmbH or one or more of its affiliated companies

Full-dose anticoagulation (according to local guidelines) with Vitamin K antagonist and other anticoagulation is not allowed during the trial conduct; LMWH is allowed only for prevention not for curative treatment.

Any planned surgeries are not allowed. Unplanned surgeries should be postponed whenever possible four weeks after stop of treatment. For urgent interventions patients should not be treated further and does require intense monitoring regarding wound healing and postoperative complications.

4.2.2.2 Restrictions on diet and life style

No restriction

4.3 TREATMENT COMPLIANCE

BI 836880 must be administered as an intravenous infusion under supervision of the investigator or dedicated clinical personnel.

Compliance may be also be verified by pharmacokinetic assessment. Any discrepancies will be documented in the eCRF by the investigator or designee.

Page 37 of 99

Trial Protocol

Proprietary confidential information © 2019 Boehringer Ingelheim International GmbH or one or more of its affiliated companies

5. VARIABLES AND THEIR ASSESSMENT

5.1 TRIAL ENDPOINTS

5.1.1 Primary Endpoint(s)

The primary endpoint to determine the maximum tolerated dose (MTD) based on the number of patients presenting dose limiting toxicity (DLT) using the National Cancer Institute (NCI) Common Terminology Criteria for Adverse Events (CTCAE) V4.03, during the first course (i.e. over the first 3 weeks of treatment) and judged to be related to the study medication.

5.1.2 Secondary Endpoint(s)

• Drug related AEs leading to dose reduction or discontinuation during treatment period

5.2 ASSESSMENT OF EFFICACY

The assessment by the investigator and the local radiologist will be the basis for continuation or discontinuation of the trial in an individual patient (in addition to safety). Tumor assessment will be performed every 6 weeks after start of treatment and at the time points specified in the Flow Chart.

After the interim data base lock, frequency of tumor assessment may be adapted according to local standard of care and in agreement with the sponsor if the patient is deriving clinical benefit (e.g. CR, PR or SD > 6 months).

CT images at baseline should be performed as close as possible to the treatment start and not older than 28 days at start of treatment.

At baseline, the investigator along with the radiologist will record the target (five target lesions maximum and maximum two per organ) and non-target lesions at baseline in the eCRF before the start of treatment. The same method of assessment and the same technique should be used to characterize each reported lesion at baseline and during follow up. Lesions in previously irradiated areas may not be considered measurable at baseline unless the lesions occurred after irradiation. Response will be evaluated according to the response evaluation criteria in solid tumors (RECIST version 1.1 (R09-0262). In the event of a delay, interruption or discontinuation of treatment, tumor assessment should continue to follow the original schedule. The schedule should be followed until progression is observed or until the patient commences further treatment for disease, whichever occurs first.

Results of tumor-specific tumor markers which will be assessed routinely should be documented in the eCRF.

After the interim data base lock, documentation of tumor markers in the e-CRF is no longer required.

5.3 ASSESSMENT OF SAFETY

Dose Limiting Toxicity (DLT)

The following drug-related adverse events will qualify as Dose-Limiting Toxicities:

- CTCAE grade \geq 3 non haematological toxicity except:
 - ➤ Vomiting or diarrhea responding to supporting treatment
 - Fatigue lasting for less than 4 days
 - Transcient Grade 3 infusion reaction (i.e. if infusion- related reaction can be controlled by appropriate medication according to investigator's decision and next infusion will not be delayed for more than two weeks).
 - Any laboratory abnormality, which is considered not clinically relevant by the investigator or resolves spontaneously or can be resolved with appropriate treatment. Clinically relevant abnormalities have to be documented as AE (see Section 5.3.6)
- CTCAE grade 4 neutropenia >7 days or complicated by infection (in case of neutropenia grade 4, close observation of patient is necessary.
- CTCAE grade >3 febrile neutropenia
- CTCAE grade = 4 thrombocytopenia
- CTCAE grade > 3 thrombocytopenia with bleeding
- CTCAE grade > 3 proteinuria (urinary protein > 3.5 g/day)
- Hypertension: increase of diastolic blood pressure (BP) by 15 mmHg confirmed by second measurement or ambulatory blood pressure measurement (when indicated; e.g. white coat effect) which cannot be controlled by hypertensive medication and requires a dose reduction of BI 836880 for further treatment course.
- All related AE leading to an interruption of BI 836880 for more than 14 days until recovery to baseline.

The MTD may be considered reached if the probability that the true DLT rate is in target interval (16%-33%) is sufficiently large (for details see Section 7). The DSB may recommend stopping the dose finding phase after the criterion for MTD is fulfilled.

If the next dose level is recommended by the statistical model, however, the efficacy is considered sufficient at current dose level, the DSB may decide to include additional number of patients at this dose level and declare this dose as RP2D and no further dose escalation will happen.

Based on the overall data after all patients on proposed RP2D have been treated for at least 1 course, the DSB will make a final determination of RP2D.

Page 39 of 99

13 Mar 2019

Trial Protocol Proprietary confidential information © 2019 Boehringer Ingelheim International GmbH or one or more of its affiliated companies

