3.3.4 Removal of patients from therapy or assessments

3.3.4.1 Removal of individual patients

An individual patient is to be withdrawn from trial treatment if:

- The patient withdraws consent for study treatment or study participation, without the need to justify the decision.
- Requiring concomitant drugs that interfere with the investigational product or other trial medication (see Section 4.2.2) or patient who requires concomitant drugs, which in the opinion of the investigator may interfere with the investigational drug.
- The patient can no longer be treated with trial medication for other medical reasons (such as surgery, adverse events, other diseases, or pregnancy).
- The patient is no longer able to complete trial visit or trial-required procedures.
- A DLT occurs which does not recover to a degree that allows continuation of treatment (see Section 4.1.4) for re-treatment criteria and dose reduction scheme)
- Progressive disease (except in cases with intra-patient dose escalation, (see Section 4.1.3) or start of any new anti-cancer therapy.

A patient can have withdrawn from the trial after discussion between the Investigator and the Sponsor if eligibility criteria are violated and/or the patient fails to comply with the protocol.

All withdrawals will be documented and the reason for withdrawal recorded and discussed, as necessary, in the final Clinical Trial Report (CTR). As soon as a patient is withdrawn from the study treatment, the end of treatment visit (EoT) has to be performed if feasible. Every effort should be made to follow-up with patients in case an adverse event is still ongoing at the time of withdrawal. If a patient is withdrawn from the trial due to consent withdrawal, no further visit will be completed.

Patients who have not completed first course of BI 836880 treatment (3 weeks) for any other reason than BI 836880 related toxicities will be considered not evaluable for MTD evaluation and should be replaced.

Patient who prematurely discontinue study drug for above mentioned reasons or any other reason, should have additional follow up visits until progression, lost to follow up, treatment with another anti-cancer treatment, death and /or end of the trial whichever comes first.

Trial Protocol Page 28 of 99

Proprietary confidential information © 2019 Boehringer Ingelheim International GmbH or one or more of its affiliated companies

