5. ENDPOINT(S)

5.1 PRIMARY ENDPOINT(S)

The objective of this study is to determine the safety and tolerability of BI 836880. The primary endpoint is the determination of the maximum tolerated dose (MTD) of BI 836880 based on the number of patients with dose-limiting toxicities (DLTs) during the first treatment cycle. The DLT is defined in section 5.3 of the CTP.

The MTD is defined as the highest dose with less than 25% risk of the true DLT probability being above 33%, and may be considered reached if the probability that the true DLT rate is in target interval (16%-33%) is sufficiently large during the MTD evaluation period.

The MTD evaluation period is defined as the time within 3 weeks after first administration of study treatment.

Patients who have not completed one cycle of treatment will be replaced. Patients who were replaced during the MTD evaluation period will not be considered for MTD determination. Those patients that have completed the MTD evaluation period without having been replaced will be referred to as patients evaluable for MTD.

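### No DLT item in protocol 5.3 says how a related course-1 toxicity that ends treatment is scored, and protocol and SAP disagree on whether that patient is evaluable

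*Protocol*

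**What the plan says.** Protocol 5.3 lists the drug-related events that count as DLTs. Three items matter here.

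- The first covers CTCAE grade ≥ "3 non haematological toxicity except" four listed exceptions. It sets no condition on later dosing.
- The hypertension item needs a confirmed diastolic rise "which cannot be controlled by hypertensive medication and requires a dose reduction of BI 836880 for further treatment course".
- The last item reads "All related AE leading to an interruption of BI 836880 for more than 14 days until recovery to baseline".

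No item names permanent discontinuation. Other sections treat it as something different from an interruption. Protocol 5.2 says "In the event of a delay, interruption or discontinuation of treatment, tumor assessment should continue to follow the original schedule", protocol 4.1.4.2 separates a temporary stop from discontinuation, and SAP 7.7 speaks of interruptions that precede permanent discontinuation. The secondary endpoint in protocol 5.1.2 does count stopping: "Drug related AEs leading to dose reduction or discontinuation during treatment period".

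On evaluability, protocol 3.3.4.1 says that patients who miss completion of course 1 "for any other reason than BI 836880 related toxicities will be considered not evaluable for MTD evaluation and should be replaced". By implication, a patient stopped for related toxicity stays evaluable. SAP 5.1 has no such exception: "Patients who have not completed one cycle of treatment will be replaced". It then leaves replaced patients out of the MTD determination. SAP 7.4 excludes from the primary analysis anyone who did not complete the evaluation period for a reason other than a DLT.

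**The concern.** Two of the DLT items depend on what is later done with the drug. Uncontrolled hypertension below grade 3 is a DLT if the dose is then reduced. If the same event ends treatment, the hypertension item as written is not met, and the last item is met only if a permanent stop is read as an interruption. A treatment decision made after the toxicity can therefore determine the primary endpoint.

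The case is plausible. Protocol 2.3 expects hypertension, proteinuria and bleeding, and 3.3.4.1 lists adverse events as a reason for withdrawal. Protocol 4.1.4.1 bars a new course under uncontrolled hypertension, allows up to two weeks of re-evaluation, and then leaves further treatment to the investigator and the sponsor's monitor.

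Cohorts hold two or three patients, so one unscored event can decide whether the model permits the next dose.

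**Working it through.** **1. How each document scores the patient.** Take a patient with a related course-1 toxicity that meets no other DLT item and leads to a permanent stop. Assume that the stop does not count as an interruption under the last item.

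| Source | Evaluable? | Enters the model as |
|---|---|---|
| Protocol 3.3.4.1 with 5.3 | Yes | No DLT |
| SAP 5.1 | No, replaced | Nothing |
| SAP 7.4 | No, excluded (reason other than DLT) | Nothing |

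The SAP rows apply to a stop before course 1 is complete. A patient who completes the three weeks and is stopped at the start of course 2 for a toxicity from course 1 is evaluable under both documents, again without a DLT.

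**2. Model inputs (protocol 7.1 and Table 7.1:1).** logit p(d) = log α + β·log(d/1250). The prior on (log α, log β) is a mixture of three normals:

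- weight 0.90, means (0.740, 0.798), SDs (2, 1)
- weight 0.05, means (0.846, −0.123), SDs (2, 1)
- weight 0.05, means (−2.731, 0.193), SDs (5, 0.01)

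All correlations are 0. The posterior is proportional to prior × ∏ p(d)^x·(1−p(d))^(n−x), integrated on a grid. P(OD) = P(p(d) ≥ 0.33 | data), and a dose is allowed if P(OD) is below 0.25.

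**3. Reproducing the plan's figures (Table 10.6:1).**

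| Scenario | P(OD) at | Printed | Computed |
|---|---|---|---|
| 1 | next dose, 120 mg | 0.062 | 0.064 |
| 2 | current dose, 40 mg | 0.318 | 0.325 |
| 3 | next dose, 240 mg | 0.066 | 0.065 |
| 4 | current dose, 120 mg | 0.231 | 0.237 |
| 5 | current dose, 120 mg | 0.623 | 0.630 |
| 6 | current dose, 480 mg | 0.020 | 0.020 |
| 7 | current dose, 480 mg | 0.229 | 0.228 |
| 8 | current dose, 960 mg | 0.353 | 0.339 |

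All agree within 0.02.

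**4. One stopped patient, three scorings.** The other two patients in the cohort are taken as DLT-free. Exclusion is shown as 0/2, because protocol 3.1 allows escalation on two evaluable patients without a DLT.

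| Earlier data | Scoring | P(OD), current dose | P(OD), next dose | Next dose |
|---|---|---|---|---|
| 0/2 at 40 mg | DLT, 1/3 at 120 mg | 0.237 | 0.510 at 240 mg | barred |
| | DLT-free, 0/3 | 0.011 | 0.049 at 240 mg | allowed |
| | excluded, 0/2 | 0.019 | 0.065 at 240 mg | allowed |
| 0/2 at 40 mg, 0/2 at 120 mg, 0/3 at 240 mg | DLT, 1/3 at 480 mg | 0.228 | 0.562 at 720 mg | barred |
| | DLT-free, 0/3 | 0.020 | 0.121 at 720 mg | allowed |
| | excluded, 0/2 | 0.033 | 0.148 at 720 mg | allowed |

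With 1/3 at 120 mg, 150 mg is barred as well (0.316). The sponsor's own table already holds two of these cases: scenario 4 (1/3 at 120 mg) stays at 120 mg, and scenario 3 (0/2 at 120 mg) goes to 240 mg.

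**The case against.** **Most serious toxicity is already covered.** Related non-haematological toxicity of grade 3 or more, hypertension included, is a DLT by the first item unless excepted, whatever happens to treatment. This stands. A reader might infer that any toxicity ending treatment escapes scoring, but the documents do not support that. What remains is hypertension below grade 3, together with other lower-grade or excepted events.

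**The contrast with a continuing patient is narrow.** Only the hypertension item mentions dose reduction. For other events the last item turns on a break of more than 14 days until recovery, so a patient who recovers sooner would not meet it even if kept on drug. This also stands. It would be wrong to say that, in general, the milder course counts and the stop does not; that holds clearly only for hypertension below grade 3.

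**A permanent stop might be read as an interruption of more than 14 days.** That reading is possible. However, 5.3 does not state it, and protocol 4.1.4.2, protocol 5.2 and SAP 7.7 keep the two terms apart. The references in 3.3.4.1 and 4.1.4.2 to stopping after a DLT presuppose an event already classed as one.

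**The SAP removes the patient rather than scoring a zero.** This is true for a stop within course 1, so it would be too strong to say that the patient always counts as DLT-free. Removal has nearly the same effect on the model, and the disagreement between the documents is a defect in itself.

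**The DSB decides, not the model.** The DSB reviews all safety data (protocol 3.1, 3.1.1, 7.4), and the RP2D draws on all courses (3.1). This reduces the risk of an unnoticed event. It does not settle what is fed to the model by which 7.1 defines the MTD.

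**Conclusion.** The point holds in a limited form. As written, a related course-1 toxicity that meets no other item and ends treatment has no defined DLT score, and protocol and SAP assign the same patient different evaluability. Under either document it does not enter the model as a DLT. One such patient can turn a barred escalation into an allowed one: 0.51 against 0.05 or 0.07 at 240 mg, and 0.56 against 0.12 or 0.15 at 720 mg, with the limit at 0.25.

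This rests on two assumptions: that the patient meets no other item, and that a permanent stop is not read as an interruption. The calculation shows sensitivity to one patient, not frequency. A reader might go further and put a figure on how many more trials would declare an overdose as the MTD. The documents give no rate for such stops, and the rates in Table 10.6:2 are for events that already meet the DLT definition. Treating part of them as hidden would not describe this gap, so no such share is offered.

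**What to change.** Reconcile protocol 3.3.4.1 and 5.3 with SAP 5.1 and 7.4. State once, in identical words in protocol 5.3 and SAP 5.1/7.4, two things about a patient permanently discontinued for a related toxicity arising in course 1: the DLT score and whether the patient is evaluable for the MTD. Word it so that the score does not depend on whether treatment was afterwards reduced, interrupted or stopped. The unqualified replacement sentence in SAP 5.1 has to be brought into line at the same time. Which events reach the clinical threshold for a DLT is for the sponsor to decide.

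The cost is about one sentence in each document. No new data are needed: protocol 3.3.4.1 already has withdrawal reasons recorded in the eCRF, and 5.3.6.2 already requires causality for each adverse event. Depending on the threshold chosen, a few more events may count as DLTs and escalation may be slightly slower.

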7.3 PLANNED ANALYSES

Only one analysis population will be considered for efficacy and safety analyses: the treated set. The treated set (TS) will consist of all patients who were treated with at least one single dose of BI 836880.

The primary analysis will be based on the treated set population excluding patients that have to be replaced for analysis of the MTD, see Section 3.3.4.1 for further details. No per protocol population will be used for analyses; however protocol violations will be identified and listed.

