4. CHANGES IN THE PLANNED ANALYSIS OF THE STUDY

Section 7.3.5.3 of the CTP stated that "The exploratory statistical analyses of the biomarker data will be performed separately and results will be covered in a separate report." However, the team has now decided to include the biomarker analyses as a part of CTR and section 5.4.1 and section 9 of this TSAP covers a list of the biomarkers to be analyzed and section 7.8.5 provides further details on their analysis.

TSAP for BI Trial No: 1336.6

Proprietary confidential information © 2017 Boehringer Ingelheim International GmbH or one or more of its affiliated companies

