6.3 PATIENT SETS ANALYSED

Treated set

This patient set includes all patients enrolled in the trial who were documented to have taken at least one dose of study medication.

Dose finding cohort treated set:

This patient set includes all patients enrolled in dose finding and confirmation of MTD cohort of the trial who were documented to have taken at least one dose of study medication and were evaluable for the MTD determination.

MTD Expansion cohort treated set:

This patient set includes all patients enrolled in expansion cohort of the trial who were documented to have taken at least one dose of study medication.

Tumor type expansion treated cohort set

This patient set includes all patients with selected tumor type enrolled in expansion cohort of the trial who were documented to have taken at least one dose of study medication.

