7.4 PRIMARY ENDPOINT(S)

The primary endpoint is to assess the MTD based on the number of patients presenting DLTs during the MTD evaluation period. The primary analysis is for the determination of the MTD. The purpose of this analysis is to summarize and document the data that led to the selection of the MTD. Therefore, an overall summary of DLTs (see CTP section 5.3.1 for the definition of DLTs) which occurred during the MTD evaluation period will be provided for each dose cohort from the dose finding cohort treated set. Patients, if any, who did not complete the MTD evaluation period for reasons other than DLT will be excluded from the analysis of the primary endpoint.

A summary of the number of patients with DLTs overall in any course will be also given by initial treatment and displayed in a similar format to the summary of DLTs occurring in the MTD evaluation period.

The analysis of the MTD is based on a Bayesian logistic regression model (BLRM) guided by the escalation with overdose control principle. The MTD is defined as the highest dose for a given schedule that is expected to cause less than 25% risk of the true DLT rate being above or equal to 33% during the MTD evaluation period. Estimation of the MTD during the dose escalation phase of the study will be based upon the estimation of the posterior probability of the incidence of DLT in toxicity categories during the MTD evaluation period for all evaluable patients. The model to be used is specified in CTP section 7.

The posterior probabilities that the toxicity rates of each dose level fall into the categories specified in CTP section 7 will be displayed.

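### SAP 5.1 replaces every cycle-1 non-completer and drops them from the MTD, without the related-toxicity exception that protocol 3.3.4.1 sets for the primary analysis

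*Protocol*

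**What the plan says.** Three rules decide who counts for the MTD.

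- **Protocol 3.3.4.1.** A patient who does not finish course 1 for "any other reason than BI 836880 related toxicities will be considered not evaluable for MTD evaluation" and is to be replaced. A patient who stops for related toxicity therefore stays in. Protocol 7.3 refers to this rule when it defines the primary analysis population: "treated set population excluding patients that have to be replaced for analysis of the MTD".
- **SAP 5.1.** The replacement rule reads "Patients who have not completed one cycle of treatment will be replaced". Its consequence follows in a separate sentence: "Patients who were replaced during the MTD evaluation period will not be considered for MTD determination". Neither sentence has a toxicity exception. The same section calls a patient evaluable if the evaluation period was completed without replacement, and it defines that period by time alone, as the 3 weeks after the first dose. SAP 6.3 restricts the dose finding cohort treated set to patients who "were evaluable for the MTD determination".
- **SAP 7.4.** For the primary endpoint the rule is: "Patients, if any, who did not complete the MTD evaluation period for reasons other than DLT will be excluded from the analysis". This spares a DLT, but no other related toxicity.

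SAP 4, which lists departures from the protocol's analysis, contains one item: "the team has now decided to include the biomarker analyses as a part of CTR".

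On timing, protocol 5.1.1 counts DLTs over the first 3 weeks. Protocol 3.1 updates the model once each patient has had a DLT or at least one course without one. One DLT criterion in protocol 5.3 is "All related AE leading to an interruption of BI 836880 for more than 14 days until recovery to baseline".

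**The concern.** The MTD comes from a small dose-toxicity dataset in which one patient can change the permitted dose. A patient who leaves course 1 because of the drug carries the information that the model needs. Protocol 3.3.4.1 keeps that patient and SAP 5.1, as worded, does not. An analyst who follows SAP 5.1 and 6.3 would build a primary dataset other than the one protocol 7.3 describes, and SAP 4 would give no warning of it. If the lost patient had a DLT, the estimated DLT rate is too low and the overdose criterion is looser than intended.

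**Working it through.** **1. The rules applied to a patient who permanently stops drug in week 2**

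| Reason for stopping | Protocol 3.3.4.1 | SAP 5.1 / 6.3 | SAP 7.4 |
|---|---|---|---|
| DLT that is not reversible (protocol 4.1.4.2 then ends treatment) | kept | removed | kept |
| Related AE that is not a DLT | kept | removed | removed, unless observation to day 21 counts as completing the period |
| Unrelated reason | removed | removed | removed, with the same proviso |

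In the first row the SAP disagrees with itself as well as with the protocol. In the second row SAP 5.1 disagrees with the protocol, and SAP 7.4 does so on one of its two readings. For a patient who skips an infusion but is observed to day 21, neither document defines completion.

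**2. Reproducing the plan's own figures**

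Inputs from protocol 7.1: logit p(d) = log α + β·log(d/1250), with the three-component prior of Table 7.1:1. The weights are 0.90, 0.05 and 0.05. The means are (0.740, 0.798), (0.846, −0.123) and (−2.731, 0.193). The SDs are (2, 1), (2, 1) and (5, 0.01), with zero correlations. P(overdose) is the posterior probability that the DLT rate is at least 0.33, obtained by grid integration. The limit is 0.25.

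| Table 10.6:1 | Computed | Stated |
|---|---|---|
| Scenario 1, at 120 mg | 0.064 | 0.062 |
| Scenario 3, at 240 mg | 0.065 | 0.066 |
| Scenario 4, at 120 mg | 0.237 | 0.231 |
| Scenario 5, at 120 mg | 0.630 | 0.623 |
| Scenario 6, at 480 mg | 0.020 | 0.020 |
| Scenario 7, at 480 mg | 0.227 | 0.229 |

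The agreement is close enough to use the model for counterfactuals.

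**3. Removing one patient who had a DLT**

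| Other data | Affected cohort: kept → removed | Dose judged | P(overdose): kept → removed | Decision |
|---|---|---|---|---|
| 40: 0/2 | 120 mg: 1/3 → 0/2 (scenario 4 becomes scenario 3) | 240 mg | 0.510 → 0.065 | changes |
| 40: 0/2, 120: 0/2, 240: 0/3 | 480 mg: 1/3 → 0/2 | 720 mg | 0.562 → 0.148 | changes |
| 40: 0/2, 120: 0/3, 150: 0/3 | 180 mg: 1/3 → 0/2 | 240 mg | 0.13 → 0.009 | same (allowed) |
| 40: 0/2, 120: 0/3, 240: 0/6 | 480 mg: 3/6 → 2/5 | 480 mg | 0.49 → 0.288 | same (barred) |
| 40: 0/2, 120: 0/3, 240: 0/6 | 480 mg: 2/6 → 1/5 | 480 mg | 0.218 → 0.078 | same (allowed; 720 mg barred at 0.662 and 0.409) |

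**4. Removing one patient who had no DLT**

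After clean 40, 120 and 240 mg cohorts, 480 mg at 0/3 becomes 0/2. P(overdose) at 720 mg rises from 0.121 to 0.148. The shift is small and on the cautious side.

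**5. Timing of the interruption criterion (secondary)**

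More than 14 days is first reached 15 days after the clock starts. The start of the clock is not defined. For infusions missed within course 1:

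- From the last dose given (day 1 or 8): 1 + 15 = day 16; 8 + 15 = day 23.
- From the missed dose (day 8 or 15): 8 + 15 = day 23; 15 + 15 = day 30.

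One of these four falls by day 21. If infusions 2 and 3 come 2 days early (days 6 and 13), the days are 16 and 21, and 21 and 28, so three of four fall by day 21. Protocol 5.3.3 says what happens to an unresolved case only for grade 4 neutropenia.

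**The case against.** **SAP 7.4 governs.** It specifies the primary analysis and keeps a patient with a DLT. SAP 3 bases itself on protocol Section 7, which leads back to 3.3.4.1, and replacement is a conduct decision taken under the protocol. A reader might infer that the SAP will discard DLT patients. The documents do not support that: it happens only if SAP 5.1 and 6.3 are followed over SAP 7.4. The objection does not settle the matter, because SAP 7.4 draws its summary from the SAP 6.3 set and its model from evaluable patients, a term that SAP 5.1 defines.

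**The time-based period.** SAP 5.1 defines the period by time, and patients who stop drug remain under AE collection. SAP 7.4 may therefore keep someone who stops for a related AE and is observed to day 21. This stands, but it leaves the SAP 5.1 wording on completing a cycle of treatment untouched.

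**Direction of the effect.** Removing a patient without a DLT raises P(overdose), so it is not true that every such removal favours escalation. This stands. The large contrasts all need a lost DLT.

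**Other safeguards.** SAP 6.2 leaves exclusions to a report planning meeting, and Table 6.2:1 excludes no one for non-compliance or for missing DLT information. Those entries concern protocol violations and do not alter the replacement rule. All-course summaries and DSB review would expose a late or dropped DLT but would not put it into the course-1 model.

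**SAP age.** The SAP is dated 20 June 2017, before the current protocol. The visible amendment entries show no change to 3.3.4.1, so age is not shown to explain the difference.

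**Timing.** A reader might infer that the criterion on interruptions over 14 days cannot work in a 21-day window. The documents do not support that. Protocol 7.3.4 assigns AEs by start date, and under an onset reading the criterion works. Protocol 3.1 sets a minimum observation time, and the DSB charter, which is not among the documents, may contain a rule.

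**Conclusion.** The replacement and evaluability rules conflict, and the conflict reaches the primary dataset. SAP 5.1 and 6.3 contradict protocol 3.3.4.1 for any related-toxicity non-completer. They also contradict SAP 7.4 when the reason is a DLT. SAP 4 does not declare the difference. It should be corrected before the MTD analysis.

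The size depends on who is lost. One lost DLT patient can carry P(overdose) across 0.25 (0.56 to 0.15 at 720 mg, 0.51 to 0.065 at 240 mg), but three of the five configurations examined give the same decision. Losing a patient without a DLT moves it slightly the other way (0.12 to 0.15). These figures assume one affected patient and the published prior. The documents give no rate at which this would occur, so no expected bias can be stated. The attribution of an interruption still open at day 21 is missing detail, not an error.

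**What to change.** 1. Align the replacement, evaluability and exclusion wording of SAP 5.1, 6.3 and 7.4 with protocol 3.3.4.1.
2. State that a patient with a DLT in the MTD evaluation period is never replaced or excluded.
3. Define completion for a patient who misses or stops drug but is observed to day 21.
4. If the SAP 5.1 rule is intended, declare it in SAP 4 and amend protocol 3.3.4.1.
5. As a clarification, reconcile protocol 3.1, 5.1.1 and 5.3 with SAP 5.1 on two points: how an interruption of more than 14 days still open at day 21 is attributed, and from which day it is counted. The clinical DLT criteria stay unchanged.

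The cost of items 1 to 4 is wording only. Item 5 is also wording. If the chosen convention is to wait for open cases, a cohort decision would occasionally be delayed, for infusions missed in course 1 by up to 9 days on the nominal schedule (day 30 − day 21).
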